#### 5.3.3. Safety Population

The safety population will include all participants who received at least 1 dose of INCB054707 or placebo during the PC period. Treatment groups for this population will be determined according to the actual treatment the participant received on Day 1 regardless of assigned study treatment.

All safety analyses for the PC period will be conducted using the safety population.

#### 5.3.4. Open-Label Evaluable Population

All analyses for the OLE period will be conducted with the open-label evaluable population, which includes all participants who received at least 1 dose of INCB054707 75 mg during the OLE period.

#### 5.3.5. Long-Term Evaluable Population

All analyses for the LTE period will be conducted with the long-term evaluable population, which includes all participants who received at least 1 dose of INCB054707 during the LTE period.

## 6. **BASELINE, EXPOSURE, AND DISPOSITION**

Appendix A provides a list of data displays. Sample data displays are included in a separate document.

## 6.1. Demographics, Baseline Characteristics, and Disease History

The demographics, baseline characteristics, and disease history will be summarized by treatment groups and overall.

### 6.1.1. Demographics and Baseline Characteristics

The following demographics will be summarized for the ITT population, the open-label evaluable population, and the long-term evaluable population: age, sex, race, ethnicity, weight, height, BMI, BMI category (< 25 kg/m^2,  $\ge$  25 to < 30 kg/m^2,  $\ge$  30 to < 40 kg/m^2,  $\ge$  40 to < 50 kg/m^2,  $\ge$  50 kg/m^2), and geographic region (North America, Outside of North America).

The following demographics will be summarized for the ITT population only: tobacco use (never used, current user, former user), cannabis use (never used, current user, former user), and alcohol use (yes, no).

### 6.1.2. Baseline Disease Characteristics and Disease History

The following baseline disease characteristics and disease history summarized for all participants in the ITT population include but are not limited to:

- Disease duration (years)
- Prior therapy or surgical intervention administered for HS
- HS family history
- Comorbidities
- Hurley stage (Stage I, Stage II, Stage III) (See Section 7.2.5 for patient overall Hurley stage)
- AN count
- AN count category
- ANF count
- Inflammatory nodule count
- Abscess count
- Draining fistula count
- Draining fistula count category
- Number of anatomical areas with abscess, inflammatory nodule or draining fistula

Note: Disease duration (years) will be calculated as follows:

Disease duration (years) = (date of randomization – date of initial HS diagnosis + 1) / 365.25.

#### 6.1.3. Medical History

For participants in the ITT population, medical history will be summarized by assigned treatment groups. This summary will include the number and percentage of participants with medical history for each body system/organ class as documented on the eCRF.

## 6.2. Disposition of Participant

The following categories will be summarized by treatment groups and overall for the ITT population in the PC period:

- Number (%) of participants who were randomized
- Number (%) of participants who were treated in the PC period
- Number (%) of participants who completed treatment in the PC period through Week 16
- Number (%) of participants who discontinued study treatment with a primary reason for discontinuation in the PC period
- Number (%) of participants who withdrew from the study with a primary reason for withdrawal in the PC period

The number of participants enrolled by country and/or site will also be provided by treatment group and overall.

The following categories will be summarized by treatment groups and overall for the open-label evaluable population in the OLE period:

- Number (%) of participants who were treated in the OLE period
- Number (%) of participants who completed treatment in the OLE period through Week 52
- Number (%) of participants who discontinued the study treatment with a primary reason for discontinuation in the OLE period
- Number (%) of participants who completed the study through Week 56
- Number (%) of participants who withdrew from the study with a primary reason for withdrawal in the OLE period

The following categories will be summarized by treatment groups and overall for the long-term evaluable population in the LTE period:

- Number (%) of participants who were treated in the LTE period
- Number (%) of participants who completed treatment in the LTE period through Week 100
- Number (%) of participants who discontinued the study treatment with a primary reason for discontinuation in the LTE period
- Number (%) of participants who completed the study through Week 104
- Number (%) of participants who withdrew from the study with a primary reason for withdrawal in the LTE period

### 6.3. **Protocol Deviations**

Protocol deviations recorded on the eCRF will be summarized by treatment groups and overall for ITT population in the PC period, open-label evaluable population in the OLE period, and long-term evaluable population in the LTE period, and listed.

### 6.4. Exposure

For participants in the safety population in the PC period, the open-label evaluable population in the OLE period, those who take INCB054707 75 mg throughout study participation up to Week 52, and the long-term evaluable population in the LTE period, study drug exposure in terms of duration of treatment with study drug will be summarized by treatment groups descriptively as follows:

• **Duration of treatment with study drug (days):** date of last dose of study drug – date of first dose of study drug + 1.

Note that the date of first and last dose of study drug are period-specific and defined in Table 3.

Treatment Period	Treatment Group	First Dose Date	Last Dose Date
PC period	Placebo INCB054707 15 mg INCB054707 45 mg INCB054707 75 mg	Date that the first dose of study drug (INCB054707 or placebo) was administered to the participants in the PC period	Date that the last dose of study drug (INCB054707 or placebo) is administered to the participants in the PC period
OLE period	Placebo to INCB054707 75 mg INCB054707 15 mg to 75 mg INCB054707 45 mg to 75 mg INCB054707 75 mg	Date that the first dose of study drug (INCB054707 75 mg) was administered to the participants in the OLE period	Date that the last dose of study drug (INCB054707 75 mg) is administered to the participants in the OLE period
Throughout study participation up to Week 52	INCB054707 75 mg	Date that the first dose of study drug (INCB054707 75 mg) was administered to the participants in the PC period	Date that the last dose of study drug (INCB054707 75 mg) is administered to the participants throughout study participation up to Week 52
LTE period	INCB054707 ≤ 45 mg INCB054707 ≥ 60 mg	Date that the first dose of study drug (INCB054707) was administered to the participants in the LTE period	Date that the last dose of study drug (INCB054707) is administered to the participants in the LTE period

Table 3:	Definition	of First and	Last Dose Date
1 4010 01	Dennition	of I hove which	

In addition, for the safety population in the PC period and the open-label evaluable population in the OLE period, average daily dose of INCB054707 and total actual dose of INCB054707 taken will be summarized by treatment groups descriptively as follows:

- Average daily dose of INCB054707 (mg/day): total actual INCB054707 dose taken (mg) / [duration of treatment with study drug (days) number of interrupted days with study drug].
- Total actual dose of INCB054707 taken (mg) will be calculated as: (total number of tablets dispensed total number of tablets returned) ×15 (mg/tablet) ×  $p_T$

Where  $p_T$  denotes the proportion of INCB054707 among the 5 tablets taken daily with  $p_T = 0$  (0/5) for placebo group, 1/5 for INCB054707 15 mg group, 3/5 for INCB054707 45 mg group, and 1 (5/5) for INCB054707 75 mg group.

Total number of tablets dispensed and returned in each period is based on information entered on the Drug Accountability eCRF. If there is dispensed drug that has not been returned yet, the actual dose taken starting from the dispense date of the unreturned drug will be imputed by the dose taken as reported on the Dosing eCRF.

## 6.5. Study Drug Compliance

For participants in the safety population, the open-label evaluable population, and the long-term evaluable population, overall compliance (%) for INCB05707/placebo will be calculated for all participants as follows:

compliance (%) =  $100 \times [\text{total dose actually taken (in the specific period)}] / [total prescribed dose].$ 

Total prescribed dose is defined as the sum of the doses prescribed by the investigator accounting for dose modifications.

Total dose actually taken will be calculated as: total number of tablets dispensed – total number of tablets returned (see Section 6.4 for details on total number of tablets dispensed and returned).

## 6.6. Prior and Concomitant Medication

Prior medications and concomitant medications will be coded using the WHO Drug Dictionary. The number and percentage of participants in the ITT during the PC period for each prior and concomitant medication will be summarized by treatment groups and overall by WHO drug class and WHO drug preferred term. For the open-label evaluable population in the OLE period and the long-term evaluable population in the LTE period, only concomitant medications will be summarized by WHO drug class and WHO drug preferred term.

## 7. EFFICACY

Appendix A provides a list of data displays. Sample data displays are included in a separate document.

## 7.1. General Considerations

For participants who enter the OLE period and do not continue in the LTE period, all by-visit analyses for open-label evaluable population will include the follow-up period if the data are available, unless otherwise specified.

For participants who continue into the LTE period, all by-visit analyses for long-term evaluable population will include the follow-up period if the data are available, unless otherwise specified.

Unless otherwise stated, the strata identified in the randomization process will be used in all efficacy analyses.

## 7.2. Efficacy Parameters

An example of the lesion count worksheet is provided in the Study Manual and will be used for assessment of AN and ANF counts, HiSCR, IHS4, and Hurley Stage. It includes assessment of 7 anatomic regions:

#### 7.2.1. AN and ANF Counts

The AN count is defined as the sum of abscess and inflammatory nodule counts. The AN results will be used to calculate change in AN count relative to baseline, as well as AN50, AN75, AN90, and AN100, defined respectively as at least a 50%, 75%, 90%, and 100% decrease in AN count relative to baseline.

The ANF count is defined as the sum of abscess, inflammatory nodule, and draining fistula counts. The ANF results will be used to calculate the change in ANF count relative to baseline.

#### 7.2.2. Hidradenitis Suppurativa Clinical Response

A HiSCR definition is based on the following criteria relative to the baseline at each visit:

- at least 50% reduction in AN count,
- no increase in abscess count, and
- no increase in draining fistula count.

HiSCR75 is defined as at least 75% reduction from baseline in AN count with no increase in the number of abscesses or draining fistulas.

HiSCR90 is defined as at least 90% reduction from baseline in AN count with no increase in the number of abscesses or draining fistulas.

#### 7.2.3. International Hidradenitis Suppurativa Severity Score System

The IHS4 (Zouboulis et al 2017) is a composite, dynamic score and validated tool used to determine HS severity. The total IHS4 score can be calculated as:

IHS4 (points) = (number of inflammatory nodules  $\times$  1) + (number of abscesses  $\times$  2) + (number of draining tunnels [draining fistulae/sinuses]  $\times$  4)

And the IHS4 category is defined as:

Mild HS:  $\leq$  3points; Moderate HS: 4-10 points; Severe HS:  $\geq$ 11 points.

#### 7.2.5. Hurley Stages of Hidradenitis Suppurativa

The Hurley Stages are defined in Table 4. The investigator (or designee) will determine the Hurley Stage in each affected anatomical region at the designated study visits. If more than 1 stage is present in the region, the worst stage in that region should be documented. The participant will be assigned an overall Hurley Stage corresponding to the stage of the worst involved anatomical region.

Hurley Stage	Description
Ι	Abscess formation, single or multiple, without sinus tracts and cicatrization (scarring).
Π	One or more widely separated recurrent abscesses with tract formation and cicatrization (scarring).
III	Multiple interconnected tracts and abscesses across the entire area, with diffuse or near diffuse involvement.

 Table 4:
 Hurley Stages of Hidradenitis Suppurativa

#### Incyte Corporation INCB 54707-204 Statistical Analysis Plan

## 7.3. Efficacy Hypotheses

The primary hypothesis is that INCB054707 75 mg is superior to placebo at Week 16 on mean change from baseline in AN in participants with HS. Assuming  $\mu_T$  is the mean change from baseline at Week 16 in AN count in INCB054707 75 mg group and  $\mu_C$  is the mean change from baseline at Week 16 in AN count in placebo group, the primary hypothesis of the study are as follows:

- $H_0$  (null hypothesis):  $\mu_T = \mu_C$
- $H_A$  (alternative hypothesis):  $\mu_T \neq \mu_C$

## 7.4. Analysis of the Primary Efficacy Parameter

The primary efficacy endpoint is the mean change of AN count at Week 16 relative to baseline.

#### 7.4.1. Primary Efficacy Analysis

#### 7.4.2. Subgroup Analyses for Primary Endpoint

Subgroups will be formed based on the following participant characteristics and baseline variables for those participants whose data are available:

- Geographic region (North America, Outside of North America)
- Baseline Hurley Stage (Stage I, Stage II, Stage III)

The primary efficacy endpoint will be summarized using descriptive statistics based on the ITT population for the subgroups defined above.

#### 7.4.3. Sensitivity and Supportive Analyses for Primary Endpoint

The primary endpoint will be analyzed using the PP population as a sensitivity analysis to the ITT.

## 7.5. Analysis of the Secondary Efficacy Parameters

#### 7.5.1. Analysis of the Key Secondary Efficacy Endpoint

The key secondary efficacy endpoint is proportion of participants who achieve HiSCR at Week 16 will be conducted for the ITT population.

#### 7.5.2. Analysis of Other Secondary Efficacy Endpoints

All other secondary efficacy endpoints are listed in Table 1 and will be summarized using descriptive statistics based on the ITT population.

For categorical measurements, summary statistics will include sample size, frequency, and percentages. For continuous measurements, summary statistics will include sample size, mean, median, standard deviation, minimum, and maximum. Summary statistics for continuous measures will be provided for baseline, the actual measurements at each visit, and the change from baseline at each visit.

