2.1.2. Scientific Rationale for Study Design

Recent literature suggests that the cytokines IL-1β, IL-17, IL-23, IL-10, and, to a lesser extent,

Adalimumab (Humira[®]), a TNF-α fully human monoclonal antibody administered

via subcutaneous injection, was approved in 2015 by the FDA for the treatment of moderate to severe HS in patients 12 years of age and older and currently remains the only approved therapy. Given the modest response rates observed with adalimumab treatment (42% and 59% vs placebo 26% and 28%, respectively in each of the Phase 3 trials) and the significant dropout rates in existing studies due to lack of efficacy (27% to 50%; Frew et al 2020), additional treatments for HS patients are needed.

In the proposed study, the clinical efficacy and safety of 3 doses (15, 45, and 75 mg) of INCB054707, a small molecule JAK1 inhibitor, will be evaluated in adult participants with HS

Version 2

and compared with placebo for 16 weeks. Since HS is a chronic inflammatory disorder, all participants will enter the 36-week OLE period to evaluate the long-term safety and efficacy of INCB054707 in HS (up to 52 weeks in total). Participants will receive INCB054707 75 mg QD in the OLE period. To further evaluate long-term safety and efficacy of INCB054707 in HS, all eligible participants will have the option to continue treatment for an additional 48 weeks (LTE period). Participants who are currently tolerating INCB054707 in the OLE, as assessed by the investigator, and who demonstrate willingness and ability to comply with the scheduled visits, will be considered eligible for the LTE period.

The primary efficacy endpoint is based on the count of AN, as this appears to be a relevant measure of INCB054707 anti-inflammatory activity. The AN count also serves as the basis of the key secondary endpoint, HiSCR, which is defined as at least a 50% decrease in AN count with no increase in the number of abscesses or draining fistulas, relative to baseline. Participants who experience rapid abscess formation at diseased sites will receive appropriate rescue treatments.

It is expected that the outcome of this study will be instrumental in the selection of a single treatment regimen to be evaluated in a Phase 3 study.

Version 2

CONFIDENTIAL

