6.6.4.2. Number of Rescue Interventions

The number of rescue interventions during each study period are provided below.

During the placebo-controlled period:

- Total of 2 Protocol-allowed interventions.
- An intervention can occur on maximally 2 different lesions at the same visit or on the same lesion at 2 different study visits.
- The same lesion cannot be treated 2 times at the same visit.
- If a participant requires more than 2 interventions within the first 16 weeks, then they must be withdrawn from the study.

During the OLE or LTE periods:

- Maximum of 2 interventions every 4 weeks.
- An intervention can occur on 2 different lesions at the same visit or on the same lesion at 2 different study visits.
- Within each 4-week period, the same type of intervention cannot be used 2 times on the same lesion.
- If a participant requires more than 2 interventions within a 4-week period or has 2 of the same interventions on the same lesion within that period, then they must be withdrawn from the study.

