10.3. Level of Significance

10.4. Statistical Analyses

10.4.1. Primary Analysis

All other secondary variables will be summarized using descriptive statistics. For categorical measurements, summary statistics will include sample size, frequency, and percentages. For continuous measurements, summary statistics will include sample size, mean, median, standard deviation, minimum, and maximum. Summary statistics for continuous measures will be provided for baseline, the actual measurements at each visit, and the change and percentage change from baseline at each visit, if applicable.

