#### Table 1:Objectives and Endpoints

Objectives	Endpoints	
Primary		
To determine the efficacy of INCB054707	• Mean change of AN count at Week 16 relative to baseline.	
Secondary		
To further evaluate the efficacy of INCB054707	• Key secondary endpoint: Proportion of participants who achieve HiSCR at Week 16. Hidradenitis suppurativa clinical response is defined as at least a 50% decrease from baseline in AN count with no increase in the number of abscesses or draining fistulas.	
	• Proportion of participants who achieve HiSCR at each visit from Weeks 2 to 12.	
	• Proportion of participants who achieve at least a 75% decrease from baseline in AN count with no increase in the number of abscesses or draining fistulas from Weeks 2 to 16.	
	• Mean change from baseline in the severity of the disease, as assessed by the IHS4 score, from Weeks 2 to 16.	
	• Proportion of participants achieving AN50, AN75, AN90, and AN100 (at least 50%, 75%, 90%, and 100% reduction in AN count relative to baseline, respectively) from Weeks 2 to 16.	
	• Mean change in AN count at Weeks 2 to 12, relative to baseline.	
	• Proportion of participants with a total AN count of 0 to 2 from Weeks 2 to 16.	
	• Mean change in draining fistula count from Weeks 2 to 16, relative to baseline.	
	• Mean change in ANF count from Weeks 2 to 16, relative to baseline.	

Objectives	Endpoints
To evaluate the safety and tolerability of INCB054707	• Frequency and severity of AEs, including the evaluation of clinical laboratory results, vital signs, ECGs, and the results of physical examinations.

Objectives	Endpoints

Objectives	Endpoints

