#### 4.1.4. Handling of Missing and Incomplete Dates

In general, values for missing dates will not be handled unless methods for handling missing dates are specified in this section or relevant sections. The original reported dates collected on the eCRF should be used in all relevant listings. The following rules will be used for handling partial dates for analyses requiring dates.

When calculating the time since diagnosis of HS, a partial HS diagnosis date will be handled as follows in the calculation:

- If only the day is missing, then the first day of the month will be used.
- If both the month and day are missing, then 01 JAN of the year will be used.
- If the diagnosis date is completely missing, then the time since diagnosis will not be calculated.

When the date of the last dose is used in deriving variables such as duration of treatment or TEAE flag, a missing or partial date of the last dose will be handled as follows:

- If only the day is missing, then the earlier date of the last day of the month or the date that the participant discontinued treatment will be used.
- If both the month and day are missing, then the earlier date of 31 DEC of the year or the date that the participant discontinued treatment will be used.
- Otherwise, the date that the participant discontinued treatment will be used as the date of the last dose.

For response endpoints, all nonresponders, as well as all participants who are missing postbaseline values, will be defined as nonresponders for the NRI analysis.

For continuous endpoints, any participant who is missing postbaseline values may have missing data handled using MMRM under the missing-at-random assumption. Mixed model repeated measures implicitly adjusts for missing data through a variance-covariance structure.

For other endpoints, missing observations will be handled as detailed in the specific sections addressing each analysis.

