## 5. STATISTICAL METHODOLOGY

### 5.1. General Methodology

Unless otherwise noted, SAS® software (SAS Institute Inc, Cary, NC; v9.1 or later) will be used for the generation of all tables, graphs, and statistical analyses. Descriptive summaries for continuous variables will include but not be limited to the number of observations, mean, standard deviation, median, minimum, and maximum. Descriptive summaries for categorical variables will include the number and percentage of participants in each category.

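### Committing to the MMRM that the SAP already permits for change in IHS4 and ANF, with a placebo difference and a nominal interval, would be a cheap improvement on raw by-visit summaries

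*SAP*

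**What the plan says.** SAP Section 7.5.2 deals with every secondary endpoint other than Week 16 HiSCR in one sentence: "All other secondary efficacy endpoints are listed in Table 1 and will be summarized using descriptive statistics based on the ITT population". For continuous measures it lists sample size, mean, median, standard deviation, minimum and maximum, by visit. Protocol Section 10.4 agrees: "All other secondary variables will be summarized using descriptive statistics". The continuous endpoints concerned, from SAP Table 1, are:

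- "Mean change from baseline in the severity of the disease, as assessed by the IHS4 score, from Weeks 2 to 16";
- change in ANF count and in draining fistula count over the same visits;
- change in AN count at Weeks 2 to 12.

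Two general passages bear on this. SAP Section 5.1 leaves the list of statistics open ("Descriptive summaries for continuous variables will include but not be limited to the number of observations") but promises no contrast between arms. SAP Section 4.1.4 says of continuous endpoints that "any participant who is missing postbaseline values may have missing data handled using MMRM under the missing-at-random assumption". That is a permission, and Section 7.5.2 does not use it. For response endpoints, the same section counts participants with missing values as nonresponders in the nonresponder-imputation analysis.

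On dropout, Protocol Section 6.6.4.2 states: "If a participant requires more than 2 interventions within the first 16 weeks, then they must be withdrawn from the study". Protocol Section 6.5.2 also stops study drug when worsening disease needs a prohibited medication.

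**The concern.** A by-visit mean with no missing-data rule is in practice the mean of those still observed. If participants who do badly leave, the remaining mean looks better than the arm as a whole. If the two arms lose such participants to different extents, the difference that a reader takes from the table is biased. A reader can compute a raw difference and interval from the tabulated numbers, means and standard deviations, but both would inherit that bias.

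Protocol Section 2.1.2 expects that "the outcome of this study will be instrumental in the selection of a single treatment regimen to be evaluated in a Phase 3 study". IHS4 and ANF are supporting evidence for that choice and do not decide it. What is at stake is a slightly distorted secondary picture, shown without any measure of precision, when three doses are set beside placebo and beside each other.

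**Working it through.** **Inputs.** The documents give about 200 participants in four equal groups, so 200/4 = 50 per arm. The public copy shows no standard deviation, effect size or dropout rate for this trial, so there is no stated figure to reproduce. Protocol Section 2.1.2 cites 27% to 50% dropout for lack of efficacy in existing studies, not split by arm. Everything else below is assumed.

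**Step 1: what drives the bias.** Suppose the worst fraction q of an arm leaves, judged on a score with correlation ρ to the outcome. The observed mean then shifts by −ρ·φ(z)/(1−q) standard deviations, where z is the (1−q) normal quantile.

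- q = 0.27: z = 0.613, φ = 0.331, ratio 0.331/0.73 = 0.453.
- q = 0.10: z = 1.282, φ = 0.175, ratio 0.175/0.90 = 0.195.

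With ρ = 0.7 and 27% loss on placebo against 10% on active, the difference moves by 0.7 × (0.453 − 0.195) = 0.18 SD towards zero. With the same q and the same mechanism in both arms the two shifts cancel. So the bias in the contrast depends on how the arms differ in outcome-related loss.

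**Step 2: one mechanism for every arm.** The withdrawal rule is the same in all arms, so the natural case is a common hazard. The simulated set-up was:

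- visits at Weeks 2, 4, 6, 8, 12 and 16, correlation 0.9 per 2 weeks, SD 6 to 8;
- Week 16 AN change −2.5 on placebo and −5.5 on active, with 94% of it reached by Week 12, so the true Week 12 difference is 0.94 × (−5.5 + 2.5) = −2.82;
- hazard after each visit logistic in the AN change at that visit, log-odds 0.6 or 1.2 per SD, the same in both arms, with average dropout of 20% or 30%.

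Dropout came out at about 21%/19% to 34%/26% (placebo/active), because placebo participants do worse. The raw Week 12 difference shrank by 0.07 to 0.30 lesions, always towards zero. That is 0.07/2.82 = 2% to 0.30/2.82 = 11%. Against a standard error of about 1.51 (50 per arm, SD 7, simulated with 30%/15% dropout), it is 0.30/1.51 = 0.2 SE or less. A steeper dependence of dropout on outcome than 1.2 would enlarge the understatement in the same direction.

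**Step 3: equal dropout.** Forcing 30% in both arms with the same mechanism (log-odds 1.2) gave true/raw −2.81/−2.82 at SD 6 and −2.83/−2.86 at SD 8, so almost no bias.

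**Step 4: arm-specific dropout, for contrast.** Log-odds 1.2, Week 12 AN:

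| Dropout placebo/active | SD | True | Raw | MMRM |
|---|---|---|---|---|
| 30%/15% | 6 | −2.86 | −2.30 | −2.86 |
| 30%/15% | 8 | −2.79 | −2.02 | −2.78 |
| 15%/30% | 6 | −2.82 | −3.44 | −2.84 |
| 15%/30% | 8 | −2.83 | −3.62 | −2.83 |

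At 50 per arm and SD 7, the 30%/15% case gives a raw mean of −2.16. The shift is 0.66 lesions, 0.66/1.51 = 0.44 SE, and a raw 95% interval would cover Φ(1.96 − 0.44) − Φ(−1.96 − 0.44) = 0.93. MMRM recovers the truth here because dropout was simulated as missing-at-random. That does not show that the assumption holds in the trial.

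**Step 5: precision.** With 50 per arm the 95% half-width for a difference is 1.96 × √(2/50) = 0.39 SD. With 36 per arm (27% lost) it is 0.46 SD. On an assumed IHS4 SD of 15, the first is 0.39 × 15 = 5.9 points. The tables as planned do not display this uncertainty.

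**The case against.** The strongest reply is that nothing is broken. The protocol and SAP agree that these endpoints are descriptive, no inference is claimed from them, and the primary and key secondary endpoints are handled separately. Section 4.1.4 already names MMRM for continuous endpoints. Parts of the SAP, including the text of Section 7.4.1, are not visible; if the primary model is a repeated-measures model, AN at Weeks 2 to 12 may already come from it. All of this stands. It makes the point an optional improvement that rests mainly on IHS4 and ANF.

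A second reply also stands in part. Protocol Table 3 puts the early-termination visit (ET1), with lesion counts, in the Week 16 column, and Protocol Sections 7.1.2 and 8.7 call for that visit at discontinuation. Leavers may therefore contribute a count under Week 16, and it cannot be taken as settled that they are absent from that column. That count would be an earlier measurement under a later label, so its assignment needs stating.

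A reader might go further and infer that the raw tables could flatter the drug, or bias different doses in opposite directions. Step 4 shows what that would require: poor responders leaving an active arm more readily than placebo. The documents give no arm-specific dropout, and the rule that they do give is common to all arms.

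**Conclusion.** The point holds as a cheap improvement and is not an error in the plan. For IHS4 and ANF, the visible text commits to raw by-visit summaries with no placebo difference, interval or firm missing-data rule, although the SAP already names a suitable method.

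The likely consequence is a small understatement of the drug-placebo difference: about 2% to 11% for AN at Week 12, 0.2 SE or less. This rests on an assumed effect, standard deviation, visit correlation, dropout level and strength of outcome dependence. AN serves as the worked example; no common-mechanism figure was computed for IHS4 or ANF. Within that range, a larger shift, or any overstatement, needs dropout that differs by arm in ways the documents do not show.

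It would also be wrong to infer that the primary result is in doubt. The primary test is not affected. The responder endpoints have their own nonresponder rule.

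**What to change.** In SAP Section 7.5.2:

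- State that the MMRM of Section 4.1.4 applies to change in IHS4 and ANF count, and to AN at Weeks 2 to 12 only if the Section 7.4.1 model does not already provide it.
- Report by visit the least-squares mean change, the difference from placebo and a nominal 95% confidence interval labelled as unadjusted for multiplicity, with the observed number in each arm.
- Assign ET1 lesion counts to a visit by their actual date, not automatically to Week 16.
- Keep the raw tables as support. Leave draining fistula count descriptive unless its distribution supports the model.

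The cost is SAP wording and a little more programming. No test is added, so no alpha is spent. The estimates rely on missing-at-random, which the SAP should say beside them.
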